Title: Outpatient Recovery from acute Kidney Injury requiring Dialysis (ORKID)

NCT Number: NCT05158153

Date: 4/17/23

Outpatient Recovery from acute Kidney Injury requiring Dialysis (ORKID) Protocol

Summary: There are currently no therapies to improve the chances of recovering enough kidney function to come off of dialysis after severe acute kidney injury. It is not known if current routine outpatient dialysis treatments are optimized to maximize the chances of recovery. This is a single-center (multi-clinic), single-arm, non-randomized pilot study to investigate the feasibility, tolerability, and safety of a bundled intervention (cooled dialysate, high sodium dialysate, high dose diuretics, high ultrafiltration hold threshold, active dialysis weaning) designed to foster recovery from acute kidney injury requiring dialysis.

Inclusion Criteria:

- AKI-D, attributed at least in part to acute tubular necrosis by clinical nephrology team
- Age \geq 18 years
- Pre-hospitalization eGFR \geq 15 mL/min/1.73m²
- Being discharged to a participating outpatient dialysis unit (within 30 miles of UCSF)

Exclusion Criteria:

- Known loop diuretic allergy/intolerance
- Dialysis duration $>$ 3 months
- Pregnant, Prisoner, or Unable to consent
- Clinical team declines to allow approach for study

Intervention: During the 90-day study period, participants will be prescribed outpatient hemodialysis with cooled dialysate (35-36°C), high sodium dialysate (145 mmol/L), a high ultrafiltration hold threshold (systolic blood pressure $>$ 110 mmHg; ultrafiltration hold threshold will not be applied in participants with baseline systolic blood pressure $<$ 120 mmHg), and high dose diuretics (160 mg oral furosemide twice daily) to be taken every day at home will also be prescribed. Dialysis will be weaned according to an active weaning protocol.

Outcomes:

- Primary: Feasibility – the proportion of patients who received the dialysate temperature, dialysate sodium concentration, diuretic dose, and ultrafiltration hold threshold that was ordered at least once in the first two weeks of treatment.
- Secondary: Tolerability - the proportion of enrolled patients completing the 90-day study still continuing each intervention. Safety - Incidence of adverse events including electrolyte abnormalities, emergent dialysis treatments, and hospitalizations. Time to renal recovery - Days after study enrollment before renal recovery, defined as being alive and off dialysis for 14 consecutive days. Intradialytic hypotension – proportion of dialysis sessions with nadir systolic blood pressure $<$ 90 mmHg. Recruitment rate - number of participants enrolled per month. Screening-to-recruitment ratio - ratio of the number of participants who meet inclusion criteria to the number of participants enrolled. Modified dialysis symptom index score. Kidney disease quality of life-36 score.

Statistical Analysis Plan: We will perform descriptive statistics on the outcome variables.

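### Does defining intradialytic hypotension per dialysis session, with session counts that depend on weaning and recovery, leave the outcome undefined or misleading?

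*Combined protocol and SAP*

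**What the plan says.** The Outcomes section lists intradialytic hypotension as a secondary outcome in its own right: the "proportion of dialysis sessions with nadir systolic blood pressure" below 90 mmHg. Its denominator is sessions. Two neighbouring outcomes count people instead. The primary feasibility outcome is a proportion of patients, and tolerability is "the proportion of enrolled patients completing the 90-day study still continuing each intervention".

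Two other statements mean that session counts will vary between participants. Under Intervention: "Dialysis will be weaned according to an active weaning protocol". Under Outcomes, renal recovery is "defined as being alive and off dialysis for 14 consecutive days". The window is 90 days.

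The Statistical Analysis Plan is one sentence: "We will perform descriptive statistics on the outcome variables". It sets out no pooling rule, participant-level summary, interval or test. The Summary describes the trial as a "single-arm, non-randomized pilot study to investigate the feasibility, tolerability, and safety of a bundled intervention".

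**The concern.** A participant's number of sessions is partly an outcome of the study. Someone who comes off dialysis early contributes few sessions, and someone who does not recover may contribute throughout the 90 days. Pooling all sessions therefore weights participants by how long, and how often, they are dialysed, which is what the bundle is meant to change. If hypotension is more frequent in those who stay on dialysis, the pooled figure lies above the average participant's rate. If it is less frequent in them, the pooled figure lies below.

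The trial has no control arm, so the figure would be read as an absolute statement about the bundle, with no contrast in which the weighting might cancel. A single pooled percentage also cannot show whether hypotension was spread over most participants or concentrated in a few with many sessions. Because the plan does not state the weighting, this looks at first like an undefined outcome in a study concerned with tolerability and safety.

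**Working it through.** The plan has no figure to reproduce. It states no sample size, session frequency, recovery proportion or expected hypotension rate, so every number below is an assumption chosen to show the range.

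**Identity.** Let participant *i* have *m_i* sessions and hypotension rate *p_i*, with *N* participants.

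- Pooled rate = Σ *m_i p_i* / Σ *m_i*
- Participant average = Σ *p_i* / *N*
- Pooled minus average = Cov(*m*, *p*) / mean(*m*)

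The gap is zero when session count and rate are uncorrelated. Otherwise it takes the sign of their covariance.

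**Central illustration.** Half recover after 12 sessions and half have 39 (three a week for 13 weeks).

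| Rate, recoverers / others | Pooled | Average | Gap (points) |
|---|---|---|---|
| 10% / 30% | (12×0.10 + 39×0.30)/51 = 12.9/51 = 25.3% | 20.0% | +5.3 |
| 20% / 20% | 10.2/51 = 20.0% | 20.0% | 0 |
| 20% / 10% | (2.4 + 3.9)/51 = 12.4% | 15.0% | −2.6 |
| 30% / 10% | (3.6 + 3.9)/51 = 14.7% | 20.0% | −5.3 |

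Check of the first row by the identity: mean(*m*) = 25.5 and Cov = 13.5 × 0.10 = 1.35, so the gap is 1.35/25.5 = 0.053.

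**Range with 39 sessions for non-recoverers.** Let the recovering share *w* run from 0.3 to 0.7 and recoverers' sessions from 6 to 24.

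- Rates 10%/30%: from +1.8 (*w* = 0.3, 24 sessions: 8.91/34.5 = 25.8% against 24.0%) to +8.7 (*w* = 0.7, 6 sessions: 3.93/15.9 = 24.7% against 16.0%).
- Rates 20%/10%: from −0.9 (12.1% against 13.0%) to −4.4 (12.6% against 17.0%), in the same two cells.

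**Effect of the 39-session input.** A count of 39 means full thrice-weekly dialysis with no weaning, although the protocol applies active weaning generally. If non-recoverers are partly weaned to 26 sessions (also assumed):

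- *w* = 0.5, 12 sessions, 10%/30%: 9.0/38 = 23.7% against 20.0%, a gap of +3.7 instead of +5.3.
- *w* = 0.3, 24 sessions, 10%/30%: 6.18/25.4 = 24.3% against 24.0%, a gap of +0.3.
- Same cell, 20%/10%: 3.26/25.4 = 12.8% against 13.0%, a gap of about −0.2.

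So the gap can be close to zero even when rates differ. At the other end, rates of 5% and 40% with *w* = 0.5 and 6 against 39 sessions give 15.9/45 = 35.3% against 22.5%, or +12.8 points; swapping the two rates gives −12.8. The gap scales directly with the assumed difference in rates.

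**Reading the definition.** A proportion whose denominator is sessions gives each session equal weight. That is the pooled rate, and it answers a clear question: how often a delivered treatment was complicated by hypotension. The change of unit from patients to sessions is not an inconsistency. Receiving or continuing an intervention is a fact about a patient, whereas intradialytic hypotension can occur only during a session.

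**The case for a change.** The best argument for a change is that the wording does not strictly exclude a proportion computed within each participant and then averaged, and that the two versions could differ by several points. Equal rates across participants cannot be taken for granted either. The ultrafiltration hold threshold is not applied when baseline systolic pressure is below 120 mmHg, so participants start from different pressures and do not all receive the same components. Showing both summaries would cost one sentence and one table row from data already collected.

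Much of this stands as reporting advice. Weighting by sessions does depend on weaning and recovery, and a participant-level display would show concentration that the pooled rate hides. But different baseline pressures do not establish that hypotension is related to session count, and the documents neither state nor exclude such a relation. The suggestion also keeps the planned rate and adds to it. A general commitment to descriptive statistics leaves room for that addition without amendment.

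A further argument concerns precision, since sessions within a participant are not independent. With 20 participants and 510 sessions as in the central illustration, a naive 95% half-width of 3.8 points would widen to between 6.1 and 10.2 points for assumed within-participant correlations of 0.05 to 0.20. That would matter if an interval were reported from sessions treated as independent. The plan contains no interval, so there is nothing to correct.

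**Conclusion.** The concern is arithmetically right but does not call for a change. Read in its ordinary sense, the outcome is a pooled risk per dialysis session. Followed as written, the plan yields a valid descriptive figure. The plan attaches no test, comparator, threshold or go/no-go rule to it, so no planned conclusion depends on whether the session-weighted or the participant-averaged rate is shown.

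The possible gap between the two runs from about zero to several points in either direction, and to 12.8 points at the most extreme inputs tried. All of that range rests on assumed session counts, recovery shares and hypotension rates, and on an assumed link between hypotension and session count. What the plan lacks is a label and a supplementary display, which an analyst can reasonably supply when writing up: call the rate pooled per session, and show the spread of session counts and of individual hypotension proportions beside it. The individual proportions will be noisy for participants with few sessions, which is a reason to keep the pooled rate as the main figure.
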